The gut has received much attention over the past few years for its increasing role in human health and disease. Recent research has found a correlation between host genetics and the gut genome [8-10]; with $\dot{V}O_{2peak}$ associated with greater gut microbial diversity [11-14]. Gut microbiome diversity is a marker of health and can be increased by the consumption of prebiotic fibre [15-18].

There has been minimal, if any, research to identify the association between the gut microbiome and its effect on $\dot{V}O_{2peak}$ trainability. More specifically, do individuals with a low or high response genetic profile for trainability have differing gut microbiota; and can this microbiome be positively influenced to elicit greater CRF changes for the host?

The overall objective of IMPROVE HIIT is to contribute to evidence-based personalised medicine. Understanding the factors that influence training variability could be used to improve individualised exercise prescription, thereby contributing to health maintenance and treatment/prevention of disease.

AIMS

Primary Aim

- To identify if altering the gut microbiome with prebiotic supplementation influences the $\dot{V}O_{2max}$ training response to HIIT

Primary Hypothesis

- Altering the gut microbiome will influence the $\dot{V}O_{2max}$ training response to HIIT

Secondary Aims

- To identify if the gut microbiome is correlated to the gene predictor score
- To detect if altering the gut microbiome improves chronic disease risk factors

Secondary Hypotheses

- Gene predictor scores associated with the HIIT-induced $\dot{V}O_{2max}$ training response will be correlated with a specific gut microbiota taxa.
- Manipulating the gut microbiome will improve chronic disease risk factors
- The gene predictor score will predict lower vs higher responders to the HIIT-induced $\dot{V}O_{2max}$ response

BACKGROUND

The worldwide prevalence of chronic diseases, such as cardiovascular disease, cancers, stroke and diabetes is rising [19]. Low cardiorespiratory fitness is strongly associated with chronic diseases and premature mortality [20-22]. To alleviate the health and economic burden associated with low cardiorespiratory fitness, health guidelines across the world recommend individuals undertake regular exercise training [19].

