Our gut microbiome is predetermined by host genetics that can be manipulated through numerous external factors, such as exercise and diet. Whilst host genetics and associated gut taxa increases susceptibility to various chronic diseases and overall fitness levels, the relationship between the gut microbiome and $\dot{V}O_{2max}$ trainability is unknown.

In addition to examining the gene predictor score for $\dot{V}O_{2max}$ trainability, our study will also investigate microbiota-related genes, host genes related to gut microbiome composition, and the genes involved with the gut-microbiota cross-talk. In conclusion, we hope to collect data to help understand if manipulation of the gut microbiome can improve the training response of individuals with a low gene predictor score for $\dot{V}O_{2max}$ trainability.

RESEARCH PLAN

Improving High Intensity Interval Training Response (IMPROVE-HIIT)

Overview

Improve HIIT will examine the association between the gene predictor score for $\dot{V}O_{2max}$ trainability the gut microbiome; and to investigate whether altering the gut microbiome via diet and training influences the $\dot{V}O_{2max}$ training response to HIIT.

Design

Improve HIIT is an 8-week randomised trial with two groups allocated to either: (1) HIIT plus placebo; or (2) HIIT plus prebiotic

Study Population

Consenting adults aged over 18 years.

Power Calculation (sample size justification)

The proposed project will be a pilot study. Considering financial resources, a sample size of 40 is possible. When using G*Power (download.cnet.com) ([52]), a sample size of 39 will achieve a medium effect size of 0.22 (using 6 predictors). This participant number is similar to a previous study examining if gut taxa is related to $\dot{V}O_{2max}$ levels [12]. A linear multiple regression model was used to include covariates that may contribute to the overall outcome (e.g. 6 predictors may include BMI, age, gender, initial $\dot{V}O_{2max}$, initial gut microbiome and cholesterol levels). Below are results of the power calculation:

F tests - Multiple Regression: Special (R^2 increase)

Analysis: A priori: Compute required sample size

Input:	Effect size f^2	= 0.22
	α err prob	= 0.05
	Power (1- β err prob)	= 0.8
	Numerator df	= 1
	Number of predictors	= 6
Output:	Noncentrality parameter λ	= 8.58
	Critical F	= 4.149097
	Denominator df	= 32
	Total sample size	= 39
	Actual power	= 0.8106

Recruitment

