- A diary (see appendix) will be provided to monitor supplementation compliance, and to monitor exercise attendance. This diary will also include instructions on when and how to take the supplement, and to highlight that dietary habits should not be changed during the intervention period.
- Participants will be asked what days and time-frames suit best for the 6-week exercise intervention. A tentative date will be booked for their first supervised exercise session. The two-week supplementation adjustment period will begin two weeks before this date.

Randomisation

Prior to the first testing session of the first participant, sequentially numbered opaque sealed envelopes will be used to randomly allocate participants to one of two intervention groups: 1) High intensity interval training plus placebo (maltodextrin) (HIIT-M), or 2) High intensity interval training plus prebiotic powder (HIIT-P)

'HIIT-M' written on carbon paper will be inside 20 of the opaque envelopes. 'HIIT-P' written on carbon paper will be inside the remaining 20 opaque envelopes. These 40 envelopes will be shuffled several times in the presence of at least two investigators.

Participants will be given a code to deidentify them for this study. For example, participant 'a' may have the code IMPROVE HIIT_01. Once participants have been deidentified with a code, these codes will be sequentially placed on the outside of the shuffled envelopes. This procedure will be done in the presence of all investigators involved in the study.

Participants will be blinded as to which supplement they are using. Aside from the principal investigator, researchers involved in the study will be blinded as to which supplement each participant is using. Only the principal investigator will have access to the master code.

Intervention Groups

All participants will be instructed to maintain their usual diet during the intervention period. This information will be outlined in the diary they are provided during their second visit (see appendix).

1. Supplementation adjustment period

Each group will have two weeks prior to the 6-week exercise intervention to gradually increase the dose of supplementation from 2g to 12 g/day (6g/day twice daily) by the start of the 6-week intervention. This will be done to reduce unwanted side-effects in the prebiotic supplementation group, such as flatulence.

Rationale for prebiotic

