Investigating whether altering the gut microbiome via diet and training influences the $\dot{V}O_{2max}$ training response to HIIT

The change in $\dot{V}O_{2max}$ of each participant will be calculated. Low responders will be classified by a $\dot{V}O_{2peak}$ change of <100ml of O_2 /min, and high responders by a $\dot{V}O_{2peak}$ change of > 700ml in O_2 /min (following the intervention period).

To compare the mean change in OTUs, alpha diversity, fibre intake and butyrate production to $\dot{V}O_{2max}$ training response, a one-way analysis of co-variance (ANCOVA) will be calculated (with age, sex, baseline $\dot{V}O_{2max}$ as covariates).

A multiple regression analysis will be used to evaluate the role of possible predictors for change in $\dot{V}O_{2max}$. Predictors will be screened using a Spearman correlation matrix to find the top four significant variables to include in the multiple regression analysis (e.g. gene predictor score, sex, age, gender, BMI, fibre intake, OTUs, butyrate production, alpha diversity).

The above approach will also be used to compare changes in other biomarkers (e.g. blood tests, body fat percentage etc).

All statistical tests will be performed at a 5% significance level.

1. Montero, D. and C. Lundby, *Refuting the myth of non-response to exercise training: 'non-responders' do respond to higher dose of training*. JAP, 2017.
2. Mann, T., R. Lamberts, and M. Lambert, *High responders and low responders: factors associated with individual variation in response to standardized training*. Sports Med, 2014. **44**(8): p. 1113-1124.
3. Bouchard, C., et al., *Personalized preventive medicine: genetics and the response to regular exercise in preventive interventions*. Prog Cardiovasc Dis, 2015. **57**(4): p. 337-46.
4. Rankinen, T. and C. Bouchard, *Genetic predictors of exercise training response*. Current Cardiovascular Risk Reports, 2011. **5**(4): p. 368-372.
6. Williams, C., et al., *Genes to predict VO2max trainability: a systematic review*. BMC Genomics, 2017. **18**(Suppl 8:831).
7. Astorino, T. and M. Schubert, *Individual responses to completion of short-term and chronic interval training: a retrospective study*. PLoS One, 2014. **9**(5): p. e97638.

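### The analyses that the protocol states for its primary question do not include a comparison of the prebiotic and placebo arms

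*Protocol*

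**What the plan says.** The Primary Aim reads "To identify if altering the gut microbiome with prebiotic supplementation influences the" VO2max training response to HIIT. Under Design, "Improve HIIT is an 8-week randomised trial with two groups allocated to either: (1) HIIT plus placebo; or (2) HIIT plus prebiotic". Under Randomisation, 20 envelopes are prepared for each arm.

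The Statistical Analysis section has two parts.

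- The first concerns the gene score. Its ANCOVA groups participants as expected low or high responders by gene predictor score, with age and sex as covariates.
- The second has a heading that restates the primary question. It defines low and high responders by VO2peak change (below 100 and above 700 ml/min). It then plans an ANCOVA "To compare the mean change in OTUs, alpha diversity, fibre intake and butyrate production to" the VO2max training response, with age, sex and baseline VO2max as covariates. Last comes a multiple regression for change in VO2max. Candidates are screened by Spearman correlation and the four leading significant ones are kept; the examples given are "e.g. gene predictor score, sex, age, gender, BMI, fibre intake, OTUs, butyrate production, alpha diversity".

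The same approach is then extended to blood tests, body fat and other biomarkers. Neither part names the supplement, the placebo or the allocated group.

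**The concern.** The aim is causal: does giving the prebiotic change the training response? Randomisation supports that question only through a comparison of the groups it created. The stated analyses ask instead whether people whose gut measures, fibre intake or butyrate changed more also gained more VO2max, whichever supplement they took.

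Such an association can arise without any prebiotic effect. The protocol's own Background (Exercise and the gut microbiome) reports that six weeks of aerobic training alone raised faecal short-chain fatty acids, and that the butyrate and acetate changes depended on BMI. Both arms train here, so differences in training adherence or body size could move gut measures and VO2peak together.

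Two errors are possible. A pooled association could be read as support for the hypothesis when the prebiotic does nothing. A real difference between arms could go untested. Because the approach is carried over to the other biomarkers, the secondary aim on chronic disease risk factors has the same gap. Nor is there a stated test of whether the prebiotic altered the gut relative to placebo.

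**Working it through.** **1. Where arm could enter, analysis by analysis**

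| Stated analysis | Grouping or predictors | Arm present? |
|---|---|---|
| Gene-score ANCOVA | Low vs high by gene score; age, sex | No |
| Primary-question ANCOVA | Gut, fibre and butyrate change against VO2max response; age, sex, baseline VO2max | No |
| Primary-question regression | Four screened variables from an open list of examples | Not listed; if added, could be screened out |
| Other biomarkers | Same approach | No |
| Power calculation | "6 predictors may include BMI, age, gender, initial" VO2max, initial gut microbiome and cholesterol | Not listed; the one tested predictor is unnamed |

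**2. The protocol's sample-size figure**

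Inputs (Power Calculation): f² = 0.22, α = 0.05, power 0.80, numerator df 1, 6 predictors.

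- Denominator df = N − 6 − 1 = 39 − 7 = 32.
- λ = f² × N = 0.22 × 39 = 8.58.
- Critical F(1, 32) = 4.149.
- Power from the non-central F = 0.8106. N = 38 gives 0.7998, so 39 is the smallest N.

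The stated figures reproduce exactly. They power one unnamed regression term and are not tied to the arm contrast.

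**3. The same calculation with arm as the tested term**

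Model: arm, age, sex and baseline VO2max (4 predictors), N = 40, 1:1 allocation, so f² = d²/4 with d in residual SDs.

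- Denominator df = 40 − 4 − 1 = 35; λ = 0.22 × 40 = 8.8; power = 0.822.
- The protocol's f² = 0.22 corresponds to d = 2√0.22 = 0.94.
- Power of 80% needs f² = 0.208, that is d = 2√0.208 = 0.91.
- The protocol gives no dropout rate. If 36 participants were evaluable (assumption), power at f² = 0.22 would be 0.778 and the detectable d 0.96. With 32 (assumption), 0.725 and 1.03.

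**4. Illustration of what a pooled association can show**

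Assumptions: 20 per arm; no prebiotic effect on VO2peak or on the gut measure; gut change and VO2peak change correlate at r for reasons unrelated to arm; both bivariate normal; two-sided 5% test. The documents give no value for r. Results are by simulation.

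| r | Pooled correlation significant | Arm comparison significant |
|---|---|---|
| 0.1 | 9% | 5% |
| 0.2 | 24% | 5% |
| 0.3 | 48% | 5% |
| 0.4 | 74% | 5% |
| 0.5 | 92% | 5% |

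If the prebiotic shifts the gut measure by an assumed 0.8 SD but still does not affect VO2peak, the pooled figures at r = 0.3, 0.4 and 0.5 are 41%, 66% and 87%; the arm comparison stays at about 5%. Treating gut change as a fixed predictor (non-central F) gives slightly higher values: 49%, 77% and 94% at r = 0.3, 0.4 and 0.5.

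**The case against.** Several points can fairly be made for the protocol.

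- **A separate analysis plan may exist.** This stands as a limit on the claim. A reader might infer that no arm comparison is planned anywhere; the protocol alone cannot show that. It shows only that none is stated here. Deferral does not explain the gap, however, because the protocol fixes models, covariates and a selection rule for this very question.
- **The predictor lists are examples.** Arm could be added to the regression. It would then stay in the model only if it ranked among the leading screened variables, and a randomised contrast that may be dropped is not a planned test of the primary hypothesis.
- **Other sentences hint at group comparisons.** Nutrition analysis mentions an interaction between dietary and supplemental inulin, which would need allocation, but no model follows and VO2max is not its outcome. The Kruskal-Wallis fallback compares undefined data sets.
- **There is adjustment.** The ANCOVA includes baseline VO2max, BMI and fibre intake are candidate predictors, and diet recall is collected to control for diet. A reader might infer that the associations are wholly uncontrolled; they are not. Adjustment for measured factors still does not replace randomisation.
- **The protocol sets no decision rule and calls itself a pilot.** So it cannot be said that a significant association would certainly be reported as confirming the hypothesis. The section heading nevertheless ties these analyses to it.

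**Conclusion.** The point holds for the protocol as written: it poses a randomised question and specifies analyses for it that do not use the randomised contrast. That conclusion rests on the text and on no calculation.

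The percentages are an illustration only. They run from 9% to 92% as the assumed r goes from 0.1 to 0.5, so they depend almost wholly on an unsourced input. They also describe a simple pooled correlation, not the covariate-adjusted ANCOVA or the screened regression. A reader might take a single figure such as 74% as the false-positive rate of the planned analysis; the documents do not support that.

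The sample-size arithmetic is correct on its own inputs. An arm-based analysis needs no larger sample if the protocol's f² = 0.22 is accepted as the arm effect, but that is a large difference (0.94 residual SD). This should be corrected before analysis, since otherwise the primary hypothesis has no stated test.

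**What to change.** - **Primary analysis.** Name an ANCOVA of VO2peak (post-intervention value or change) on randomised arm, HIIT-P against HIIT-M, adjusted for baseline VO2peak, age and sex. Analyse participants as randomised and report the adjusted difference with its 95% CI.
- **Withdrawals.** Reconcile this with the Withdrawal Criteria section, under which the data of people who withdraw are destroyed. Report the number lost in each arm.
- **Gut measures and risk factors.** Use the same arm-based model for alpha diversity, butyrate and the other gut measures, and for each risk factor.
- **Associations.** Keep the gut-response ANCOVA and regression as exploratory, with arm in the model and not subject to screening. An exploratory arm by gene-score term is optional.
- **Power statement.** Identify arm as the tested term and say that 40 participants give 80% power only for a difference of about 0.9 residual SD, with less after dropout.

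**Cost.** The models need only a change of wording, because every variable is already collected. The withdrawal rule needs an actual decision, as it determines whether all randomised participants can be analysed. The power statement makes plain that a moderate prebiotic effect could easily be missed.

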However, in human studies, there has been a mixed response to treatment prebiotics [43]. The variability in response is often dependent upon dose, host genetics, total fiber intake compared to overall kilojoule intake, chain length of the fructans, and the initial amount and type of bifidobacteria strain within the gut [16, 43, 45]. Thus, measuring SCFA in addition to microbiome diversity is warranted.

Table 1. Summary of studies using inulin type fructans

Study Design	Results	Reference
Healthy adults given either 5 or 7.5g of agave inulin/day for three weeks compared to control (no supplementation). N=29.	Actinobacteria and Bifidobacterium were significantly increased in the inulin group compared to the control group ($p=0.001$). Butyrate was positively associated with total fiber intake ($p=0.005$) and bifidobacterial abundance ($p=0.08$)	[46].

15 obese women received 16g of ITF per day for 3 months, compare to those (n=15) who took a maltodextrin/placebo (16g/day).	Bifidobacterium and Caecalibacterium prausnitzii were significantly increased in ITF group (p=0.01). Fecal propionate and acetate were lower in the ITF group, which correlated with a lower BMI	[47]
Jerusalem artichoke inulin or chicory inulin snack bars (7.7g/day for one week; twice daily for 2 weeks) compared to placebo (ordinary snack bars). N=15 in each group – 45 in total.	Increased prevalence of bifidobacterial and reduced Bacteroides/Prevotella in inulin group compared to a placebo (p<0.05). There were no changes in fecal SCFA concentrations	[48]
Critically ill patients received 7g of ITF for 7 days. n=22.	No difference in gut changes	[49].
ITF mixture compared to a placebo (6g of maltodextrin twice daily) for one week before and three weeks after radiotherapy. N=31.	Increased prevalence of Lactobacillus and Bifidobacterium species in ITF group (p=0.03).	[50].
Cross-over design with a 2-week wash out period. 4 weeks of chicory-derived inulin (12g/day), compared to placebo (12g maltodextrin/day). N=42.	Bifidobacterium and Anaerostipes abundance was increased, and Bilophila decreased in inulin group (p<0.05).	[51].

Conclusion

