Change in cardiorespiratory fitness

An incremental treadmill test to exhaustion on a treadmill will be completed at baseline and 6 weeks to ascertain $\dot{V}O_{2peak}$. This test involves the participant wearing a head and mouthpiece, nose tape and nose clip. The participant walking on a treadmill at 0% gradient and 1.6km/hour (Bruce Ramp). This initial stage is used as the warm up period. During the test, speed and gradient is monitored. Heart rate and rating of perceived exhaustion is measured at the end of every minute. The speed and or gradient of the treadmill is increased every one-minute. Expired air is collected via a metabolic cart every 30 seconds during the test. Heart rate is measured via a Polar heart rate monitor and blood pressure is taken using a sphygmomanometer. The participant is encouraged to exercise until exhaustion. At exhaustion, the grade, speed and heart rate are recorded. The workload is decreased to 3km/hour with no incline to allow the participant to cool down. Following the cool down, the test is ended, and all devices are removed from the participant. $\dot{V}O_{2peak}$ is measured as the average of the two highest volumes of oxygen consumed (reported as volume per minute relative to body weight; mL/kg/min).

STAGE	TIME (min)	GRADE (%)	SPEED (km/hr)
1	1	0	1.6
2	1	5	2.1
3	1	10	2.7
4	1	10	3.4
5	1	11	3.7
6	1	12	4.0
7	1	12	4.2
8	1	13	5.0
9	1	14	5.4
10	1	14	6.1
11	1	15	6.6
12	1	16	6.7
13	1	16	7.2
14	1	17	7.7
15	1	18	8.0
16	1	18	8.5

Figure 2. VO_{2peak} test stages

Gut microbiota

Gut diversity/bioinformatics and short-chain fatty acid (SCFA) analysis will be performed on faecal samples collected at baseline and 6 weeks. Participants will be provided with a home stool collection kit with instructions. They will be asked to keep stool sample frozen until their next testing visit. After this time, the stool samples will be kept at -80 degrees Celsius until analysis. One stool sample will be kept for short chain fatty acid analysis, and two other stool samples will be sent to *Microba* for testing.

a) Short chain fatty acid analysis

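### The ANCOVA of gut and diet change against VO2max training response omits the analysed measure's own baseline, which costs precision and, if the starting gut is related to response, can bias the result

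*Protocol*

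**What the plan says.** The model is in the Protocol, Statistical Analysis, under the heading on whether altering the gut microbiome influences the VO2max training response. It is introduced as "To compare the mean change in OTUs, alpha diversity, fibre intake and butyrate production to" VO2max training response, and the method is "a one-way analysis of co-variance (ANCOVA) will be calculated (with age, sex, baseline" VO2max as covariates). Just before it, low responders are defined by a VO2peak "change of <100ml of O_2 /min, and high responders by a" change above 700 ml/min. The section closes with "All statistical tests will be performed at a 5% significance level".

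Other sections bear on the missing covariate:

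- **Gut microbiota (Data Collection):** "Gut diversity/bioinformatics and short-chain fatty acid (SCFA) analysis will be performed on faecal samples collected at baseline and 6 weeks". The table of measures also marks diversity, short-chain fatty acids and both diet instruments as pre and post.
- **Power Calculation:** the six predictors that the model may include are given by example and end with "initial gut microbiome and cholesterol levels".
- **Pre-and-probiotics:** the variable response to prebiotics is said to depend on several factors, among them "the initial amount and type of bifidobacteria strain within the gut".

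**The concern.** A raw change score is usually negatively correlated with its own starting value. Leaving that value out has two possible effects.

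The first is loss of precision. Variation in change that the baseline would explain stays in the residual.

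The second is bias. The comparison is by observed training response and not by randomised arm, so nothing balances the starting gut across lower and higher responders. If the two are related, the change score carries part of that relation into the result. Baseline VO2max is the natural baseline for a model of VO2max change, but it does not do this job for gut change.

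The section relates gut change to training response through this model and a later regression. The regression does not clearly repair the omission. Its predictors are the top four from a Spearman screen, and its example list does not say that starting gut values are candidates. The same approach is then extended to the other biomarkers, so the omission may carry over to them.

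**Working it through.** **The plan's own figure.** The R² increase test has f²=0.22, 6 predictors and 1 tested. At N=39, the denominator df is 39−6−1=32, λ=0.22×39=8.58, the critical F is 4.149 and power is 0.8106. N=38 gives 0.7998, so 39 is the smallest sufficient size. The figure reproduces and is not in dispute. It is for a multiple regression; the Protocol gives no power figure for this ANCOVA.

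**Inputs.** From the Protocol: N=40, two-sided 5%, covariates age, sex and baseline VO2max. Assumed, because the Protocol gives neither: the pre/post correlation ρ of the gut measure and the correlation r of starting gut with training response. Response is continuous, all 40 complete, and the three planned covariates are unrelated to gut and response. Simulation used 3,000 trials per setting.

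**1. Precision when r=0.** Let B be the standardised baseline, F=ρB+√(1−ρ²)·e the follow-up, and D=F−B. Then Var(D)=2(1−ρ) and Var(D given B)=1−ρ². The ratio is (1+ρ)/2, which is 0.75 at ρ=0.5 and 0.85 at ρ=0.7. Simulated error stays near 5% with or without B. Power at ρ=0.5, without B and then with B:

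- true slope 0.35: 52% and 65%
- true correlation 0.4 with the part of gut change independent of baseline: 56% and 69%

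Hence about 55% against 68%.

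**2. Response related to the starting gut state, no true link to change.** With R=rB+noise, Cov(D,R)=−(1−ρ)r and corr(D,R)=−r√((1−ρ)/2). At ρ=0.5 and r=0.4 the slope is −0.5×0.4=−0.20 (simulated −0.199).

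| ρ | r | False positives, as planned | With gut baseline |
|---|---|---|---|
| 0.5 | 0 | 4.4% | 4.4% |
| 0.5 | 0.2 | 9.3% | 5.4% |
| 0.5 | 0.3 | 15.5% | 4.9% |
| 0.5 | 0.4 | 21.0% (22% in a second run) | 5.0% |
| 0.7 | 0.2 | 7.3% | 5.4% |
| 0.7 | 0.3 | 10.4% | 4.8% |
| 0.7 | 0.4 | 15.6% | 4.5% |

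With a median split of response in place of the continuous value (ρ=0.5), the planned model gives 11.7% at r=0.3 and 15.2% at r=0.4.

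With a true slope of 0.35 and r=0.3, the planned model estimates about 0.35−(1−ρ)×0.3, which is 0.14, 0.20 and 0.26 at ρ=0.3, 0.5 and 0.7. Power is 11%, 22% and 49%, against 51%, 60% and 76% with the baseline added.

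**3. Response related only to a stable gut trait, no true link.** Now B=T+e₁ and F=T+e₂, with Var(T)=ρ and R depending on T alone. Then D=e₂−e₁ is uncorrelated with R, so the planned model is unbiased. Adding B gives R the coefficient r(1−ρ)/(1−r²). At ρ=0.5 and r=0.4 this is 0.20/0.84=+0.238, as simulated.

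| ρ | r | False positives, as planned | With gut baseline |
|---|---|---|---|
| 0.5 | 0.2 | 4.9% | 10.6% |
| 0.5 | 0.3 | 4.9% | 19.3% |
| 0.5 | 0.4 | 5.4% | 32.2% |
| 0.7 | 0.2 | 5.4% | 7.6% |
| 0.7 | 0.3 | 5.0% | 11.5% |
| 0.7 | 0.4 | 4.5% | 18.8% |

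**The case against.** The strongest objection is that this is Lord's paradox. With observed groups, neither the change score nor the baseline-adjusted model is right in general, and step 3 shows adjustment creating the kind of error it is meant to remove. That stands. The error there is positive, which is the direction the trial hopes to see. One stool collection per time point makes sampling noise plausible, and the Protocol gives nothing to choose between the two settings. A reader might infer that adding the baseline simply restores the 5% level; that holds only in the setting of step 2.

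A reader might also infer that the trial presumes people with a richer starting gut train better, so that bias is certain. The Protocol does not say so. Its primary hypothesis is that altering the gut influences response, and the Conclusion of its Background calls the relation between the microbiome and trainability unknown. The secondary hypotheses, which tie the gene score both to gut taxa and to response, make some correlation plausible but do not quantify it. The bias is therefore conditional.

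The cross-sectional link that the Protocol reports is between VO2peak level and diversity, and baseline VO2max does address that. It is only a partial stand-in. With an assumed correlation of 0.45 between baseline VO2max and baseline gut, false positives in the setting of step 2 were still 17% (ρ=0.5, r=0.4) and 9% (ρ=0.7, r=0.3).

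Three smaller objections stand in part:

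- The power figures use a continuous response in all 40 and not the Protocol's responder classes, so they are not the power of the planned test.
- The initial gut microbiome is only an example predictor for a regression, and the statement on bifidobacteria concerns response to prebiotics, not training response. These passages show that the starting gut was thought relevant, no more.
- The sentence is loose about which variable is the outcome. If it is VO2max change, baseline VO2max is its proper baseline, but gut change then enters as a predictor with its own starting value still unadjusted.

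**Conclusion.** The point holds as a conditional one. The Protocol fixes a covariate list that omits the baseline of every gut and diet measure analysed. The loss of precision does not depend on any link between starting gut and response: about 55% against 68% power at ρ=0.5. Bias is possible but not established: about 9 to 22% false positives at ρ=0.5 if the starting gut state correlates 0.2 to 0.4 with response, and none at zero. The documents do not support saying that the planned model must be biased, or that the adjusted model alone is safe. All magnitudes rest on assumed correlations, N=40 complete and a continuous response.

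**What to change.** In the ANCOVA sentence of the Statistical Analysis section, add the baseline value of the measure being analysed (OTUs, alpha diversity, fibre intake or butyrate) to age, sex and baseline VO2max. Prespecify the model without it as a sensitivity analysis, and claim a link only if both models show it in the same direction. In each of the two settings above one model holds about 5%, so requiring both keeps the error near or below that.

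The cost is wording and one degree of freedom per model; no new data are needed. The agreement rule also costs power, which cannot exceed that of the weaker model (22% in the step 2 setting with ρ=0.5, r=0.3 and a true slope of 0.35). Recasting the model with post-training VO2peak as outcome and gut change as predictor, adjusted for both baselines, is an option but not required.
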